### 4.3 Evaluations at the Time of Treatment Discontinuation

At the time of treatment discontinuation all evaluations should be completed as soon as possible (see Appendix I, Schedule of Evaluations). The following should be performed upon discontinuation of study drug:

4.3.1 Complete blood count with differential and platelets.

4.3.2 Serum chemistries: liver enzymes (AST, ALT, alkaline phosphatase), BUN, creatinine, electrolytes (sodium, potassium, chloride, bicarbonate), calcium, phosphorus, glucose, total protein, albumin, bilirubin (direct and indirect), triglycerides and total cholesterol.

4.3.3 CD4 count and HIV plasma RNA viral load, and KSHV viral load.

4.3.4 Complete physical examination including: vitals signs, weight, Karnofsky performance status (Appendix II) and toxicity evaluation.

4.3.5 Blood for ACTH and cortisol.

4.3.6 KS tumor assessment. Response of KS to treatment will be assessed as described in Section 8.0. Marker lesions and other areas will be photographed (Appendix XIV).

4.3.7 Cytokine assay (Appendix IV).

#### **4.4 Post-treatment Evaluation and Evaluation at Early Discontinuation of Therapy**

Thirty days after discontinuation of therapy, a follow-up visit will include the following procedures: complete physical examination (including vitals signs, weight, and tumor assessment, and lesion photography if the response category changed), Karnofsky performance status (Appendix II), toxicity evaluation and cytokine assay.

At a subject's final study visit, the Off-Study Form will be completed and permanent discontinuation of drug will be documented.

Subjects who withdraw for toxicity reasons should be followed until the toxicity resolves/returns to baseline, or for at least 1 month, whichever is later. In addition, subjects who go off study for reasons other than toxicity should be followed for at least 1 month after discontinuing drug.

#### **4.5 Final Evaluations/Off Drug, Off Study**

Adverse experiences must be reported if the event began any time within 30 days of receiving the study treatment. Additionally, if a site learns of any incidence of death, cancer or fetal anomaly, which is possibly, probably or definitely related to the drug, at any time after the study is closed, the event should be reported to the NCI through AdEERS (see Section 6.2) within 10 calendar days of when the Investigator learns of the event. This information may provide additional insight into the safety of PTC299.

## 5.0 TREATMENT PLAN

### 5.1 Study Drug

- 5.1.1 Study Medication Description: PTC299 is manufactured following cGMP. Each capsule contains 20 mg of the active drug substance provided as size 00 hard gelatin capsules with an orange color. Excipients present in the formulation include Solutol® HS15, Gelucire® 44/14, and butylated hydroxytoluene (BHT). The drug product in the capsules appears as an opaque, off-white soft wax at room temperature.
- 5.1.2 Study Medication Packaging: PTC299 capsules will be packaged and supplied in bulk for the study. PTC299 capsules will be provided in the bulk supply bottles. Labels for bulk supply bottles will be printed in English and will contain the following information: name and potency, bottle fill count, lot number, space to enter the subject number, dosing instructions with a space to enter the number of capsules to be taken per dose, storage conditions, sponsor address, and other information as per regulatory requirements for the United States.
- 5.1.3 Storage and Stability: Bottles containing capsules of PTC299 will be shipped and stored at room temperature (~15 to 30°C). While stability of capsules stored at up to 40°C for 6 months has been confirmed, excursions to temperatures ≥38°C are not recommended because the hard gelatin capsule shell may be damaged or the waxy material in the capsules may soften. Refrigerating or freezing must be avoided since the drug may crystallize out of the solid wax matrix in the capsules. Stability data at the start of study will support the use of the drug product for ≥6 months. The AMC will be updated by PTC Therapeutics as more stability data become available.

### 5.2 Drug Orders, Transfers, Returns, and Accountability

- 5.2.1 Drug Orders: PTC 299 will be supplied free of charge by PTC Therapeutics. AMC sites will be considered qualified to receive study drug (from the local depot of PTC) as soon as the site becomes eligible for subject enrollment (i.e., all required regulatory documents have been received by the AMC Operations Center). Upon receiving an order request from an eligible site, PTC's Clinical Supplies Manager will send an e-mail notification to the site's pharmacist, Study Site Coordinator, and the study site monitor regarding the pending study drug shipment. Drug supplies will be shipped Mondays to Thursdays only. Sites should allow at least 5 to 10 working days from the day that the order is received at PTC and the day drug is to be received at the site. To order additional study drug, please contact the Study Sponsor Drug Supply Coordinator:

[name]  
PTC Therapeutics, Inc.  
[name]  
[name]  
[contact]  
[contact]  
Email: [contact]

Additional instructions regarding drug ordering, including a form for ordering study drug will be provided on the AMC website ([www.amcoperations.com](http://www.amcoperations.com)).

- 5.2.2 Drug Dispensing: The clinic pharmacist or an alternative qualified person at each participating AMC site will be responsible for dispensing study medication. The total amount of drug necessary for the 28-day treatment cycle will be dispensed to the subject at the beginning of the cycle, with written instructions on the number of capsules to be taken at each dose. A modest overage will be supplied such that subjects have sufficient drug in case of loss, spillage, or necessary deviations in scheduling clinic returns (e.g., due to inclement weather, etc).
- 5.2.3 Returns: Subjects should return all unused study medication to the study site at the end of each cycle. Appropriate source documentation confirming the amount of study drug supplied to the subjects and documenting the return of any unused drug must be maintained by the site for compliance assessments. Clinic staff will record the study medication administration information, including the exact clock time of each dose, for doses of study drug administered in the clinic or hospital.
- 5.2.4 Drug Accountability: Study personnel must ensure that all study medication supplies are kept in a secure locked area with access limited to authorized personnel. This study product must not be used outside the context of this protocol. Under no circumstances should the investigator or site personnel supply study product to other investigators or clinics, or allow the supplies to be used other than as directed by this protocol.

The investigator and/or the responsible site personnel must maintain accurate records of the receipt of all study medication shipped by PTC Therapeutics or its designee, including, but not limited to, the date received, lot number, amount received, and the disposition of all study medication. Current dispensing records must also be maintained that include the date and amount of medication dispensed, relevant batch or bottle code numbers, and study number assigned to the subject.

All used containers of study medication should be discarded according to standard institutional policy only after the study monitor has examined them. Depending upon the decision of PTC Therapeutics, unused clinical supplies must be returned to PTC Therapeutics or its designee after the study is completed. Records documenting the date of study medication destruction or shipping, relevant batch or bottle code numbers, and amount destroyed or shipped should be kept.

The Investigator, or a responsible party designated by the Investigator, must maintain a careful record of the inventory and disposition of all drugs received using the NCI Drug Accountability Record Form (DARF) (available on the CTEP home page (<http://ctep.cancer.gov>) or by calling the Pharmaceutical Management Branch at [contact]) or a site-specific form that captures the same elements as the NCI DARF.

## 5.3 Dosing

### 5.3.1 PTC299 Treatment

Each cycle with the study drug includes administration of 56 to 84 doses of PTC299 during a 4-week (28-day) period. The maximum duration of treatment is 12, 4-week cycles. PTC299 will be administered on a BID or TID schedule at approximately the same times each day. At each dose administration, the capsule number corresponding to the appropriate dose level of PTC299 is to be swallowed whole with a glass of tap water (150 to 200 mL). Subjects should be instructed not to bite or chew on the capsules. In case of breakage of the capsules in the oral cavity, an additional glass of water should be taken immediately.

On Day 1 and on Day 28 of cycle 1, the drug will be administered in the clinic with dosing appropriately timed relative to blood sampling for PTC299 PK. Thereafter, subjects will be given an adequate supply of capsules to take at home for the duration of each single cycle (28 days) of treatment.

Ideally, when given BID, doses should be taken at ~12-hour intervals (e.g., at ~7:00 AM and at ~7:00 PM) and, when given TID, PTC299 doses should be taken at ~8-hour intervals (eg, at ~7:00 AM, at ~3:00 PM, and at ~11:00 PM). If convenient for the subject, the drug may be taken during or within ~30 minutes after a meal; however, administration with food is not required. Yogurt or pudding may be taken together with the capsules in case of difficulty in swallowing. While it is realized that variations in dosing schedule may occur in the outpatient setting, the prescribed regimen (dosing intervals) should be followed as closely as possible, especially in the clinic. In particular, on study days of PK profiling, patients administered TID dosing should take the first dose immediately after the pre-dose blood draw and not dose again until all profile blood draws are completed.

### 5.3.2 Dose Escalation Rules and Definition of MTD

In Stage 1, each subject will be assigned to Dose Level 1 (40 mg/dose BID), Dose Level 2 (80 mg/dose BID), or Dose Level 3 (100 mg/dose BID) sequentially according to the dose level being explored at the time of subject enrollment. A Dose Level -1 (20 mg/dose BID) is provided in case a subject assigned to Dose Level 1 (40 mg/dose BID) requires dose reduction. In Stage 2, 8 subjects were enrolled at the Stage 1 MTD, Dose Level 2 (100 mg/dose BID). In Stage 3, each subject will be assigned to Dose Level 6 (160 mg/dose TID), or Dose Level 7 (200 mg/dose TID) sequentially according to the dose level being explored at the time of subject enrollment. Dose Level 5 (120 mg/dose TID) is provided in case a subject assigned to Dose Level 6 (160 mg/dose TID) requires dose reduction. Dose Level 4 (100 mg/dose BID) is provided in case a subject assigned to dose Level 5 (120 mg/dose TID) requires dose reduction.

During the study, dose escalation will depend on evaluations of safety in cycle 1 of therapy. The following dose escalation rules will be employed:

- Three subjects will be studied at the first dose level. If none of these three subjects experience DLT during cycle 1, then the dose will be escalated to the next higher level in the three subsequent subjects.
- If one of three subjects experiences DLT at the current dose during cycle 1, then three more subjects will be accrued at the same dose. If none of these three additional subjects experience DLT during cycle 1, then the dose will be escalated in subsequent subjects. If one or more of the three additional subjects experiences DLT in the first cycle, the MTD has been exceeded and three more subjects will be treated at the next lower dose (if only three subjects were previously treated at that prior dose).
- If two or more subjects experience DLT in the first cycle, then the MTD has been exceeded and three more subjects will be treated at the next lower dose level (if only three subjects were previously treated at that prior dose).
- No intrasubject dose escalations in subsequent cycles of therapy will be permitted.

At the first and at all subsequent dose levels, each group of three subjects within a cohort must be observed for a minimum period of at least 28 days without DLT before subsequent subjects are enrolled at the next dose level. Escalation to the next dose level can occur with the concurrence of the Protocol Chair, AMC Group Statistician, and the AMC Medical Monitor upon review of the safety data from the ongoing group of three subjects. The PTC medical monitor should be notified promptly of the dose escalation decision.

The establishment of an MTD will be based on a review of the overall first-cycle safety data by the Protocol Chair, AMC Group Statistician, and the AMC Medical Monitor. The MTD is the starting dose level at which 0/6 or  $\leq 1/6$  subjects experience DLT with the next higher dose having at least 2/3 or 2/6 subjects encountering DLT during the first treatment cycle. Effectively, the Stage 1 MTD is that dose associated with first-cycle DLT in  $< 33.3\%$  of subjects. If none of the dose levels tested is associated with 2/3 or 2/6 subjects experiencing DLT during the first treatment cycle, subjects in the Stage 2 (Section 5.3.5) of the study will be treated at a dose of 100 mg/dose BID. Similarly, in Stage 3, if neither of the 2 dose levels (160 mg/dose TID nor 200 mg/dose TID) tested is associated with at least 2/3 or 2/6 subjects experiencing DLT during the first treatment cycle, subjects in the expansion cohort will be treated at a dose of 200 mg/dose TID.

### 5.3.3 Definitions of Dose-Limiting Toxicity

The occurrence of DLTs during cycle 1 will be used to define the MTD. In cycle 1 and in subsequent cycles the occurrence of DLTs will determine the need for dose interruptions or reductions.

DLT will be defined as the occurrence of any of the following:

- Grade  $\geq 2$  PTC299-related vomiting despite maximal oral antiemetic therapy, or a requirement for intravenous (IV) antiemetics to control PTC299-related nausea and vomiting
- Grade  $\geq 2$  proteinuria

- In patients not receiving atazanavir or indinavir, change in total serum bilirubin from baseline value of Grade 0 to on-treatment value of Grade  $\geq 3$  ( $>3.0 \times \text{ULN}$ ), whether or not serum ALT or AST are elevated
- In patients receiving atazanavir or indinavir, on-treatment serum direct bilirubin  $>40\%$  of total bilirubin, whether or not serum ALT or AST are elevated
- Change in serum ALT or AST from baseline value of Grade 0 to on-treatment value of Grade  $\geq 2$  ( $>2.5 \times \text{ULN}$ )
- Change in serum ALT or AST from baseline value of Grade 1 to on-treatment value of Grade  $\geq 3$  ( $>5 \times \text{ULN}$ )
- Grade  $\geq 3$  PTC299-related toxicities (for purposes of defining the DLT, only toxicities considered by the investigator to be possibly, probably or definitely related to PTC299 will be considered).
- Failure to complete  $\geq 80\%$  of the planned 56 doses (i.e.,  $\geq 45$  doses) of a PTC299 treatment course due to PTC299-related toxicities.

Toxicities will be graded according to the CTCAE, Version 3.0. If multiple toxicities are seen, the presence of DLT will be based on the most severe toxicity experienced. At the end of each cycle, each subject must be assessed by the investigator as to whether or not the subject experienced DLT, and this information must be recorded on the Adverse Event CRF.

NOTE: If DLT is based on PTC 299-related increases in serum triglycerides or cholesterol, the increase must be confirmed in the fasting state and the grade of toxicity must be at least one grade higher than the baseline value.

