### **3.3 Number of Subjects to be Enrolled**

- 3.3.1 Three to 38 evaluable subjects will be enrolled. In Stage 1, three successive cohorts of three subjects have been enrolled at each of the following dose levels: 40 mg/dose BID, 80 mg/dose BID, and 100 mg/dose BID. An additional eight subjects have been enrolled in Stage 2 at the highest safely tolerated dose (e.g., 100 mg/dose BID) established in Stage 1 to better define the safety, antitumor activity, and biological activities of PTC299 at this dose level. Dose escalation will continue in Stage 3 for two additional successive cohorts of 3 to 6 subjects at the following dose levels: 160 mg/dose TID and 200 mg/dose TID. Once the safety profile at each level has been established based on first cycle dose-limiting toxicities (DLTs), an additional 9 to 12 subjects will be enrolled at the highest safely tolerated dose (e.g., 200 mg/dose TID) for a total number of 15 subjects at this dose level. If the dose level of 200 mg/dose TID is not well tolerated (i.e.,  $\geq 2/6$  subjects experience a first-cycle DLT), an additional 9 to 12 subjects will be enrolled at the dose level of 160 mg/dose TID for a

total number of 15 subjects at the MTD. If the dose level of 160 mg/dose TID is not well tolerated in the initial cohort (e.g.,  $\geq 2/3$  or  $\geq 2/6$  subjects experience a first-cycle DLT), 3 to 15 subjects will be enrolled at the dose level of 120 mg/dose TID. If the dose level of 120 mg/dose TID is not well tolerated (e.g.,  $\geq 2/3$  or  $\geq 2/6$  subjects experience a first-cycle DLT), a total of 9 to 15 subjects will be enrolled at the 100 mg/dose BID dose level in Stage 3. Collectively, up to 21 patients will be enrolled in Stage 3.

- 3.3.2 Estimated accrual rate: four subjects per month.

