If a subject experiences a DLT during the 28-day course of PTC299 therapy, then study drug administration can be omitted, as necessary, until the adverse event resolves or stabilizes to an acceptable degree (i.e., to < Grade 2). Thereafter, the dose of PTC299 for the remainder of the treatment course during that cycle should be reduced by one dose level; reduction to Dose Level -1 (20 mg/dose BID) may be made for subjects experiencing PTC299-related DLT at Dose Level 1 (40 mg/dose BID); and reduction to Dose Level 4 (100 mg/dose BID) may be made for subjects experiencing PTC299-related DLT at Dose Level 5 (120 mg/dose TID) and reduction to Dose Level 6 (160 mg/dose TID) may be made for subjects experiencing PTC299-related DLT at Dose Level 7 (200 mg/dose TID). Doses during missed days of treatment should not be made up (e.g., if a subject experiences an AE on Day 7 of the treatment course and the event lasts for 3 days, the reduced dose should be administered only for a further 18 days so that the total treatment course duration remains 28 days).

A new cycle of PTC299 treatment may begin when AEs or laboratory abnormalities have returned to baseline levels. If AEs or laboratory abnormalities are not resolved to baseline, week-by-week delays in initiating the new cycle of treatment should be instituted. If it takes longer than 4 weeks for the AE to resolve to baseline, protocol treatment will be permanently discontinued. Once all toxicities have returned to baseline, the next cycle of therapy can be initiated.

Subjects experiencing any of the DLTs described in Section 5.3.3 in the current cycle of therapy should have the dose in the next cycle of therapy reduced by 1 dose level; reduction to Dose Level -1 (20 mg/dose BID) may be made for subjects experiencing PTC299-related DLT at Dose Level 1; reduction to Dose Level 4 (100 mg/dose BID) may be made for subjects experiencing PTC299-related DLT at Dose Level 5 (120 mg/dose TID) and reduction to Dose Level 6 (120 mg/dose TID) may be made for subjects experiencing PTC-related DLT at Dose Level 7 (160 mg/dose TID).

In general, after a dose is reduced for PTC299-related toxicity it should not be re-escalated, even if there is minimal or no toxicity with the reduced dose. However, if further evaluation reveals that the adverse event that led to the dose reduction was not study drug-related, the dose may be re-escalated to the original dose level.

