When there is a dose modification, the subject should be notified of the change in dose and the appropriate clinic staff should instruct the subject about the revised number of study medication capsules to be used per dose according to the new dose level.

Clinical use of other anti-VEGF compounds (e.g., bevacizumab) can be associated with delayed wound healing. For this reason, subjects who require surgery or a deep invasive procedure should have PTC299 held for  $\geq 2$  weeks before the procedure, if possible, and PTC299 should be held for  $\geq 2$  weeks after the procedure, or until complete wound healing, to avoid the theoretical risk of impaired wound closure.

#### 5.3.5 Treatment in Phase 2

Once the safety profile at each dose level has been established based on first cycle DLTs in Phase 1, up to 21 additional subjects whose response to treatment can be evaluated will be enrolled in the Phase 2 portion of the study at the highest safely tolerated dose established in the Phase 1 portion to better define the safety, antitumor activity and biological activities of PTC299 at this dose level. In the Phase 2 portion of the study, Simon's 2-stage design will be used, as described in Section 11.1. Treatment will consist of 4 week cycles of therapy (56 or 84 doses) as described in Section 5.3.2. The maximum duration of treatment is 12, 4-week cycles. Definitions of DLT will be as described in Section 5.3.3. Study drug interruptions and dosage reductions will be managed as described in Sections 5.3.1 and 5.3.4.

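### The missed-dose DLT criterion is set for the 56-dose BID cycle only, so cycle-1 DLTs on the 84-dose TID schedules of Stage 3 can be under-counted

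*Combined protocol and SAP*

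**What the plan says.** The last bullet of the DLT list in Section 5.3.3 covers doses missed because of PTC299-related toxicity. Its threshold is 80% "of the planned 56 doses (i.e".), with the minimum stated as 45 doses. No other count appears.

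The plan recognises elsewhere that cycles differ in length. Section 5.3.1 states: "Each cycle with the study drug includes administration of 56 to 84 doses of PTC299 during a 4-week (28-day) period". Section 5.3.5 repeats this for Phase 2: "Treatment will consist of 4 week cycles of therapy (56 or 84 doses"). The same section then says: "Definitions of DLT will be as described in Section 5.3.3".

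Section 5.3.2 puts the Stage 3 escalation levels at 160 and 200 mg TID, with 120 mg TID as a fallback. Cycle-1 DLTs drive the decisions:

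- With one DLT among three subjects, "then three more subjects will be accrued at the same dose". Two DLTs mean that the MTD has been exceeded.
- Section 3.3 says that if two or more of six subjects have a DLT at 200 mg TID, "an additional 9 to 12 subjects will be enrolled at the dose level of 160 mg/dose TID".
- Section 5.3.4 uses the same definition for individual dosing: "Subjects experiencing any of the DLTs described in Section 5.3.3 in the current cycle of therapy should have the dose in the next cycle" lowered by one level.

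**The concern.** The criterion has a percentage and a count, and they agree only for BID. On TID they conflict, and nothing says which governs. A site that uses the count applies a much weaker test at the highest doses in the trial than was applied in Stages 1 and 2. Two sites could score the same subject differently.

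The conflict can only lose DLTs; it cannot add any. In a 3+3 scheme one subject can change the decision: 0/3 versus 1/3 decides between escalating and adding three subjects, and 1/6 versus 2/6 decides whether the dose is tolerated. At 200 mg TID that second distinction also decides where the 9 to 12 expansion subjects are treated. A subject who is not scored as a DLT also does not trigger the one-level reduction in the next cycle.

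**Working it through.** **Inputs.** 28-day cycle; 56 doses on BID and 84 on TID (Sections 5.3.1, 5.3.5); threshold 80%, count 45 (Section 5.3.3); 3+3 rule (Section 5.3.2); escalation probabilities (Section 11.1, Table 6).

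**The plan's own count.** 0.80 × 56 = 44.8, rounded up to 45. This reproduces the stated figure for BID.

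**The same rule on TID.** 0.80 × 84 = 67.2, rounded up to 68. The written count gives 45/84 = 53.6%.

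| Schedule and rule | Minimum completed | Missed doses that make a DLT | Days of dosing |
|---|---|---|---|
| BID, as stated | 45 of 56 | 56 − 45 + 1 = 12 | 12/2 = 6.0 |
| TID, 80% | 68 of 84 | 84 − 68 + 1 = 17 | 17/3 = 5.7 |
| TID, count of 45 | 45 of 84 | 84 − 45 + 1 = 40 | 40/3 = 13.3 |

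The two TID readings disagree for subjects who complete 45 to 67 doses (17 to 39 missed).

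**Effect on escalation.** For a DLT probability p, P(escalate) = (1−p)³ + 3p(1−p)⁵. At p = 10% to 60% in steps of 10 this gives 0.906, 0.709, 0.494, 0.309, 0.172 and 0.082, which reproduces Table 6 (0.91, 0.71, 0.49, 0.31, 0.17, 0.08).

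Let c be the DLT rate counted under the 45-dose reading and g the further share of subjects in the gap. The 45-dose reading gives P(c); the 80% rule gives P(c+g). The documents give no value for g, so 2, 5 and 10 percentage points are assumptions.

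| c | Count of 45 | 80% rule, g = 2 points | g = 5 points | g = 10 points |
|---|---|---|---|---|
| 10% | 0.906 | 0.871 | 0.814 | 0.709 |
| 20% | 0.709 | 0.665 | 0.600 | 0.494 |
| 30% | 0.494 | 0.454 | 0.396 | 0.309 |

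At g = 0 the columns coincide. The chance that six subjects include at least one in the gap is 1 − (1−g)⁶, or 11%, 26% and 47% for the three values of g.

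**Can a subject fall in the gap?** Yes. Section 5.3.4 treats vomiting on dosing as a missed dose that is not made up. Section 5.3.3 counts related vomiting as a DLT only at Grade 2 or above despite maximal oral antiemetics, or when intravenous antiemetics are needed. A TID subject who loses one dose a day this way on 17 days, below that threshold, completes 84 − 17 = 67 doses (79.8%). That is a DLT under 80% but not under the count of 45.

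**The case against.** The strongest reply is that the bullet states an 80% principle and 45 is only its value for 56 doses, so a sensible investigator would use 80% of 84. That reading is natural, but the text names a fixed denominator and a fixed count, and Section 5.3.5 imports both without comment.

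Second, the exposed group is small. Related Grade 3 events and several Grade 2 events are already DLTs. Section 5.3.4 provides for omitting drug once a DLT has occurred, lets dosing continue through sub-DLT liver changes, and asks for a retest within 72 hours when liver values reach DLT level (about 9 TID doses, below 17). This stands: the gap is mainly persistent lower-grade toxicity, skipped doses and ad hoc holds. The 10-point case at c = 10% would need as many gap-only DLTs as all the others together, so it is an upper illustration. At 2 points the shift is only about 0.04. The formula also bears on just one planned upward TID step, 160 to 200 mg.

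Third, there are safeguards. Section 5.3.2 says "Escalation to the next dose level can occur with the concurrence of the Protocol Chair, AMC Group Statistician, and the AMC Medical Monitor" after safety review. Section 5.3.4 holds a new cycle until events return to baseline. Section 11.2 summarises dose omissions with reasons. These make an overlooked case less likely, but none tells the investigator, who scores DLT each cycle, or the reviewers which threshold applies on TID.

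**Conclusion.** The concern holds. The missed-dose criterion is right for BID and has no valid count for the TID schedules on which Stage 3 escalates. If the count of 45 is applied, the toxicity-related time off drug needed for a DLT rises from 5.7 to 13.3 days, more than double, at the highest doses studied.

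Under-counting is possible, not certain. It requires that someone uses the count instead of the percentage, and that a subject misses 17 to 39 doses for related toxicity without another DLT. The effect on escalation depends on assumed gap rates: a fall of roughly 0.04 to 0.20 in the escalation probability under the 80% rule across the values tried, and none if the gap is empty. Because the error goes only towards fewer DLTs and sits in the rule that sets the dose, it should be corrected before Stage 3 DLTs are scored.

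**What to change.** Amend the last DLT bullet of Section 5.3.3 so that the threshold is at least 80% of planned doses, meaning at least 45 of 56 on BID and at least 68 of 84 on TID. Leave the requirement that the missed doses be due to PTC299-related toxicity as it stands.

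If any Stage 3 cycle-1 data already exist, re-score them against the amended text. The log in Appendix XI records morning, afternoon and evening doses for each day but not why a dose was missed, so the re-scoring must also use the adverse event records and the reasons for dose deviations, which the plan already collects. The cost is a one-line amendment with no new data collection.
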